4.6 Data Derivations and Transformations

Baseline is defined as the last non-missing value prior to the first dose of CRV431 or placebo administration.

5. STUDY SUBJECTS

5.1 Disposition of Subjects

Subject disposition including subjects randomized, subjects in each analysis set, study completion status, and reasons for early discontinuations will be summarized by presenting frequency counts and percentages for each treatment group. A by subject listing will also be provided.

A listing of informed consent and eligibility will be provided for all subjects that signed informed consent.

5.2 Protocol Deviations

Distribution for the types of protocol deviations and the number of subjects that deviate from the protocol will be tabulated for the treatment group.

5.3 Demographic Characteristics

Demographic data, consisting of subjects who provided consent for collection of a genomic sample, age, sex, ethnicity, race, weight (kg), height (cm), and body mass index (BMI) assessed at screening visit will be summarized by treatment for the Safety Set.

5.4 Medical History

All medical conditions and surgical procedures will be classified by system organ class (SOC) and preferred term (PT) using the Medical Dictionary for Regulatory Activities (MedDRA). The number and percent of subjects with each medical condition and surgical procedure will be presented for each SOC and PT for the Safety Set.

5.5 Prior and Concomitant Medications

Concomitant medications will be coded using World Health Organization (WHO) drug classifications. The number and percent of safety subjects using concomitant medications will be tabulated by Anatomical, Therapeutic, and Chemical (ATC) class 4 and by preferred name.

5.6 Non-drug Therapies

Non-drug therapies will be classified by SOC and PT using MedDRA. The number and percent of subjects with each medical condition and surgical procedure will be presented for each SOC and PT for the Safety Set. The number and percent of subjects using non-drug therapies will be presented for each SOC and PT for the Safety Set.

6. EFFICACY ANALYSIS

6.1 Primary Efficacy Endpoint and Analysis

The endpoints of this study are safety and tolerability related and therefore there are no efficacy endpoints.

6.2 Pharmacokinetic Endpoints and Analysis

[REDACTED]

[REDACTED]

6.3 Exploratory Endpoints and Analysis

[REDACTED]

[REDACTED]

[REDACTED]

[REDACTED]

- [REDACTED]
- [REDACTED]
- [REDACTED]
- [REDACTED]

7. SAFETY ANALYSIS

All safety summaries (or analyses if applicable) will be conducted using the Safety Set.

7.1 Extent of Exposure

The duration of exposure, the total exposure of CRV431, the total number of doses and capsules will be summarized and presented by visit and overall. All data will be listed.

7.2 Adverse Events

An AE is defined as any untoward medical occurrence in a clinical study subject associated with the use of a drug (investigational or non-investigational) in humans, whether or not considered drug related. An AE can be any unfavorable and unintended sign (e.g., an abnormal laboratory finding), symptom, or disease temporally associated with the use of a drug, without any judgement on causality. An AE can arise from any use of the drug (e.g., off-label use, use in combination with another drug) and from any route of administration, formulation, or dose, including overdose.

All AEs that occur after any subject has been consented, before treatment, during treatment, or up to and including the End of Study or Early Termination Visit, whether or not they are related to the study, must be recorded on forms provided by Hepion Pharmaceuticals, Inc.

7.2.1 Treatment-emergent Adverse Events

A treatment-emergent adverse event (TEAE) is defined as an AE that occurs after study drug administration.

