11.4. Recording Adverse Events

Adverse events spontaneously reported by the subject and/or in response to an open question from the study personnel or revealed by observation will be recorded during the study at the investigational site. Clinically significant changes in laboratory values, blood pressure, and pulse requiring an intervention should be reported as AEs. The AE term should be reported in standard medical terminology when possible. For each AE, the investigator will evaluate and report the onset (date and time), resolution (date and time), severity, causality, action taken, serious outcome (if applicable), and whether or not it caused the subject to discontinue the study.

Adverse events should be collected and recorded in the source documents and on the eCRF beginning at the time of signing the informed consent. Adverse events and SAEs should be reported through End of Study Visit or Early Termination Visit. Both AEs and SAEs should be followed until resolution/stabilization or until a time that is mutually agreed upon between the medical monitor and investigator.

Subjects who experience any AE or SAE should receive appropriate treatment and medical supervision as clinically indicated.

All AEs will be graded for severity according to the Common Terminology Criteria for Adverse Events table v5.0 ([CTCAE, 2017](#)).

It is important to distinguish between serious and severe AEs. Severity is a measure of intensity whereas seriousness is defined by the criteria under Section 11.2.2. An AE of severe intensity may not be considered serious.

Should a pregnancy occur, it must be reported and recorded on Hepion's pregnancy form. Pregnancy, in itself, is not regarded as an AE unless there is a suspicion that an investigational product may have interfered with the effectiveness of a contraceptive medication.

The outcome of all pregnancies (spontaneous miscarriage, elective termination, normal birth or congenital abnormality) must be followed up and documented even if the subject was discontinued from the study.

All reports of congenital abnormalities/birth defects are SAEs. Spontaneous miscarriages should also be reported and handled as SAEs. Elective abortions without complications should not be handled as AEs.

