12.3.5. Safety Analyses

All safety data will be populated in the individual CRFs. All safety data will be listed by subjects.

Adverse events will be coded using the most current version of Medical Dictionary for Regulatory Activities (MedDRA) summarized by treatment for the number of subjects reporting the treatment emergent adverse event (TEAE) and the number of TEAEs reported. A by-subject AE data listing including verbatim term, coded term, treatment, severity, and relationship to population will be provided.

Safety data including ECGs, vital signs assessments and clinical laboratory results, will be summarized by population and point of time of collection.

Descriptive statistics using appropriate summary statistics will be calculated for quantitative safety data as well as for the difference to baseline, when appropriate. In addition, a shift table describing out of normal range shifts will be provided for clinical laboratory results.

Concomitant medications will be listed by subject and coded using the most current version of WHO drug dictionary. Medical history will be listed by subject.

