7.2.5 Adverse Event Summaries

All AEs (serious and non-serious) occurring after completion of the informed consent process and before the end of study, regardless of relationship to study drug, will be included and classified by SOC and PT using the Medical Dictionary for Regulatory Activities (MedDRA).

For treatment-emergent AEs (TEAEs), the following will be summarized and presented for the safety analysis set:

- i. An overall summary of TEAEs, which includes:
 - a. the number and percentage of subjects experiencing a TEAE
 - b. the number and percentage of subjects experiencing a TEAE by strongest relationship to study medication
 - c. the number and percentage of subjects experiencing a TEAE by greatest severity
 - d. the number and percentage of subjects experiencing a TEAE leading to study withdrawal
 - e. the number and percentage of subjects experiencing a treatment emergent SAE (TESAE)
- ii. the number and percentage of subjects experiencing a TEAE by SOC and PT

- iii. the number and percentage of subjects experiencing a TEAE by SOC, PT and the highest severity
- iv. the number and percentage of subjects experiencing a TEAE by SOC, PT and the strongest relationship to study medication
- v. the number and percentage of subjects experiencing a TESAE by SOC and PT
- vi. the number and percentage of subjects experiencing a TEAE leading to study withdrawal by SOC and PT

In the overall summary of TEAEs table (i), besides tabulating the number and percentage of subjects, the total number of TEAE episodes will also be provided. If a subject has repeated episodes of a particular TEAE, all episodes will be counted in the summary table.

In the remaining summary tables, the incidence of TEAEs will be calculated by dividing the number of subjects who have experienced the event by the total number of subjects in the safety set. Thus, the incidence of TEAEs is shown in terms of the total number of subjects and not in terms of the total number of episodes. If a subject has repeated episodes of a particular TEAE, only the most severe episode, or the episode with the strongest causal relationship to study drug, will be counted in the summary tables.

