A subject with more than one type of TEAE in a particular SOC will be counted only once in the total of subjects experiencing TEAEs in that particular SOC. Since a subject could have more than one type of TEAE within a particular SOC, the sum of subjects experiencing different TEAEs within the SOC could appear larger than the total number of subjects experiencing TEAEs in that SOC. Similarly, a subject who has experienced a TEAE in more than one SOC will be counted only once in the total number of subjects experiencing AEs in all SOCs.

All occurrences of all AEs will be listed for each subject, grouped by cohort. The listing will contain the following information: treatment group, verbatim term, SOC, PT, severity, relationship to study medication, date and day of onset, date and day of resolution, treatment given to treat the adverse event, the outcome, whether the event was an SAE, whether it led to withdrawal and whether it is a TEAE. Listings will be sorted by subject identification number, onset date, SOC, and PT. If the onset date is completely missing, then these events will be presented first. If the onset date is missing a month or a day, then these events will be presented before any complete dates.

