12.2 Appendix B: List of Proposed Tables

Summary of Subject Disposition – All Subjects

Summary of Protocol Deviations – Safety Set

Summary of Demographics – Safety Set

Summary of Medical History by System Organ Class and Preferred Term – Safety Set

Summary of Prior and Concomitant Medications – Safety Set

Summary of Non-drug Therapies by System Organ Class and Preferred Term – Safety Set

Summary of Biomarkers: Change from Baseline – Safety Set

Summary of Biomarkers: Percent Change from Baseline – Safety Set

Summary of Exposure – Safety Set

Overall Summary of Treatment-emergent Adverse Events – Safety Set

Treatment-emergent Adverse Events by System Organ Class and Preferred Term – Safety Set

Treatment-emergent Adverse Events by System Organ Class, Preferred Term and Highest Severity – Safety Set

Treatment-emergent Adverse Events by System Organ Class, Preferred Term and Strongest Relationship to Study Drug – Safety Set

Treatment-emergent Serious Adverse Events by System Organ Class and Preferred Term – Safety Set

Treatment-emergent Adverse Events Leading to Study Withdrawal by System Organ Class and Preferred Term – Safety Set

Summary of Blood Chemistry Results – Safety Set

Summary of Hematology Results – Safety Set

Summary of Urinalysis Results – Safety Set

Summary of Vital Signs – Safety Set

Summary of ECG – Safety Set

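### The TEAE definition has no worsening clause, so on its plain reading an AE that starts before first dose and rises in CTCAE grade on treatment is left out of the AE tables

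*Combined protocol and SAP*

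**What the plan says.** SAP 7.2.1 is a single sentence: a TEAE "is defined as an AE that occurs after study drug administration". Protocol 12.3.5 bases its AE summary on TEAEs but does not define the term.

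Recording starts well before dosing. Protocol 11.4 states: "Adverse events should be collected and recorded in the source documents and on the eCRF beginning at the time of signing the informed consent". It also lists what is reported: "For each AE, the investigator will evaluate and report the onset (date and time), resolution (date and time), severity, causality, action taken". That list names one onset, one resolution and one severity for each AE.

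SAP 7.2.5 opens broadly, with "All AEs (serious and non-serious) occurring after completion of the informed consent process and before the end of study" to be included and coded. The summaries that follow are all narrower. Each of items i to vi concerns TEAEs or treatment-emergent SAEs, for example "the number and percentage of subjects experiencing a TEAE by SOC, PT and the highest severity". SAP Appendix B matches this: its six AE tables are all treatment-emergent, including "Treatment-emergent Adverse Events Leading to Study Withdrawal by System Organ Class and Preferred Term".

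AEs that are not TEAEs still reach the by-subject listing, which shows among other items "whether the event was an SAE, whether it led to withdrawal and whether it is a TEAE".

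**The concern.** Safety and tolerability against placebo is a primary objective (protocol 6.1), and the TEAE tables are its main AE summary. A mild symptom that appears during screening and becomes severe on drug is something those tables should show. Under the definition as written, its onset precedes dosing, so it does not qualify.

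The window is not trivial. Protocol 7.1.1 allows screening up to 30 days before Day 1, and up to 60 when a retest is requested, against 28 days of dosing. AEs that start before dosing are therefore a planned part of the database.

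Two outputs could also disagree. Protocol 8.3.1 lists AE grades that lead to discontinuation. A subject who reached one through worsening of such an AE would count as discontinued in the disposition summary (SAP 5.1), yet might be missing from the table of TEAEs leading to withdrawal.

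**Working it through.** The plan states no figure on this point, so the check is of the text, followed by simple arithmetic for scale.

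**Following one event through the plan.** Take an AE with onset after consent and before first dose, Grade 1 at first dose and Grade 3 on treatment.

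1. Is it recorded? Yes, because recording starts at consent (protocol 11.4).
2. Is the grade change recorded separately? Protocol 11.4 names one onset and one severity per AE. No visible text asks for the date of a grade change or tells sites to enter worsening as a new AE.
3. Is it a TEAE? SAP 7.2.1 looks only at whether the AE occurs after dosing. If the AE keeps its pre-dose onset, it is not a TEAE.
4. Does the highest-severity rule bring it in? No. In SAP 7.2.5 that rule chooses among episodes of an event already classed as a TEAE.
5. Which AE tables can show it? The six in SAP Appendix B are the overall summary, SOC and PT, highest severity, strongest relationship, SAEs, and those leading to withdrawal. All six are restricted to treatment-emergent events, so none can.
6. Where does it appear? In the by-subject listing (SAP 7.2.5), flagged as not a TEAE. A laboratory worsening would also show in change from baseline (SAP 7.3). Worsening of a symptom has no such second route.

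**Scale of one omission.** The inputs are the planned cohort sizes of 12, 6, 12 and 6 (protocol 7.2), with each cohort taken as its own column. The change in a row is 1/n:

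- Cohort of 12: 1/12 = 8.3 percentage points, so a row that should read 1/12 (8.3%) reads 0/12 (0%).
- Cohort of 6: 1/6 = 16.7 percentage points, so 1/6 (16.7%) reads 0/6 (0%).

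This is the change in a specific row, such as a given preferred term at Grade 3. The row for any TEAE changes only if the subject has no other TEAE.

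**The case against.** The strongest reply is that the definition says the AE occurs, not that it starts. Since SAP 7.2 defines an AE as any untoward medical occurrence, a grade increase on treatment could itself be read as a new occurrence after dosing. A site that enters it that way gives it a post-dose onset, and it is counted. SAP 7.2.5 also foresees repeated episodes of one event with different severities. This stands as a possible reading, and it is why a reader who infers that these events are certain to be missing from every table goes too far. It does not remove the gap. The outcome then depends on each site's habit, and protocol 7.3.3 leaves the investigator unblinded, so the choice would be made by someone who knows the treatment.

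A reader might also infer that the AE form has no place for a grade change, or that no other definition exists. The documents do not support either. The AE form and its instructions are not included, and parts of protocol 12.3 and SAP section 4 are redacted. What can be said is that no visible text settles the matter.

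The gap is also narrower than all pre-existing symptoms. A condition present before consent is medical history, and its worsening after dosing could be entered as an AE with post-dose onset. The exposed events are those with onset between consent and first dose.

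Finally, with 36 planned subjects and a listing that shows onset, severity, relationship and withdrawal, a careful reader could trace a mismatch between tables. That is true, but the tables should not need it.

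**Conclusion.** The point holds as a defect in the tabulation rule. The only visible definition has no worsening clause, and every planned AE table depends on it. On the plain reading, an AE that starts between consent and first dose and worsens on treatment is left to the listing. This assumes that the AE keeps its pre-dose onset and that nothing in the redacted text or the unseen form instructions says otherwise.

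One omission is worth 8.3 points in a given row of a 12-subject cohort and 16.7 points in a 6-subject cohort. How often it would happen cannot be stated. The documents give no rate, and any probability of at least one omission would only restate the rate assumed.

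A reader might infer that such events are lost altogether, or that subject protection is weakened. Neither follows. The events stay in the listing, and the criteria in protocol 7.7 and 8.3.1 rest on CTCAE grade, relationship, seriousness, and laboratory or ECG values, not on TEAE status. The change is worth making before database lock, but it is a correction to reporting and not a flaw in trial conduct.

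**What to change.** In SAP 7.2.1, define a TEAE as an AE that starts after the first dose of CRV431 or placebo, or that starts before that dose and increases in CTCAE grade after it. The six Appendix B tables then need no change in scope.

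So that the clause can be applied, instruct sites either to record the grade increase with its date or to enter the worsening as a new AE. One method should be chosen and used at all sites. The AE form completion instructions are a suitable place.

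The cost is one SAP sentence and a short recording instruction. If protocol 11.4 is edited as well, the amendment goes through ethics review (protocol 15.1). The downside is that a few events that began before dosing will enter the TEAE tables, under the same rule in active and placebo cohorts. Sample size and the clinical rules do not change.

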7.2.2 Adverse Event Severity

All AEs will be graded for severity according to the Common Terminology Criteria for Adverse Events table v5.0 (CTCAE, 2017).

7.2.3 Adverse Event Relationship to Study Medication

An investigator who is qualified in medicine must make the determination of relationship to the

investigational product, when appropriate, for each AE (unrelated, possibly related or probably related). The investigator should decide whether, in his or her medical judgment, there is a reasonable possibility that the event may have been caused by the investigational product. If no valid reason exists for suggesting a relationship, then the AE should be classified as “unrelated.” If there is any valid reason, even if undetermined, for suspecting a possible cause and effect relationship between the investigational product and the occurrence of the AE, then the AE should be considered “related.”

If the relationship between the AE/SAE and the investigational product is determined to be “possible” or “probable” the event will be considered to be related to the investigational product for the purposes of expedited regulatory reporting.

7.2.4 Serious Adverse Events

An AE is considered serious if, in the view of either the investigator or sponsor, it fulfills at least one of the following:

- Results in death
- It is immediately life-threatening
- It requires in-patient hospitalization or prolongation of existing hospitalization
- It results in persistent or significant disability or incapacity
- Results in a congenital abnormality or birth defect
- It is an important medical event that may jeopardize the subject or may require medical intervention to prevent one of the outcomes listed above.

7.2.5 Adverse Event Summaries

All AEs (serious and non-serious) occurring after completion of the informed consent process and before the end of study, regardless of relationship to study drug, will be included and classified by SOC and PT using the Medical Dictionary for Regulatory Activities (MedDRA).

For treatment-emergent AEs (TEAEs), the following will be summarized and presented for the safety analysis set:

- i. An overall summary of TEAEs, which includes:
 - a. the number and percentage of subjects experiencing a TEAE
 - b. the number and percentage of subjects experiencing a TEAE by strongest relationship to study medication
 - c. the number and percentage of subjects experiencing a TEAE by greatest severity
 - d. the number and percentage of subjects experiencing a TEAE leading to study withdrawal
 - e. the number and percentage of subjects experiencing a treatment emergent SAE (TESAE)
- ii. the number and percentage of subjects experiencing a TEAE by SOC and PT

- iii. the number and percentage of subjects experiencing a TEAE by SOC, PT and the highest severity
- iv. the number and percentage of subjects experiencing a TEAE by SOC, PT and the strongest relationship to study medication
- v. the number and percentage of subjects experiencing a TESAE by SOC and PT
- vi. the number and percentage of subjects experiencing a TEAE leading to study withdrawal by SOC and PT

In the overall summary of TEAEs table (i), besides tabulating the number and percentage of subjects, the total number of TEAE episodes will also be provided. If a subject has repeated episodes of a particular TEAE, all episodes will be counted in the summary table.

In the remaining summary tables, the incidence of TEAEs will be calculated by dividing the number of subjects who have experienced the event by the total number of subjects in the safety set. Thus, the incidence of TEAEs is shown in terms of the total number of subjects and not in terms of the total number of episodes. If a subject has repeated episodes of a particular TEAE, only the most severe episode, or the episode with the strongest causal relationship to study drug, will be counted in the summary tables.

A subject with more than one type of TEAE in a particular SOC will be counted only once in the total of subjects experiencing TEAEs in that particular SOC. Since a subject could have more than one type of TEAE within a particular SOC, the sum of subjects experiencing different TEAEs within the SOC could appear larger than the total number of subjects experiencing TEAEs in that SOC. Similarly, a subject who has experienced a TEAE in more than one SOC will be counted only once in the total number of subjects experiencing AEs in all SOCs.

All occurrences of all AEs will be listed for each subject, grouped by cohort. The listing will contain the following information: treatment group, verbatim term, SOC, PT, severity, relationship to study medication, date and day of onset, date and day of resolution, treatment given to treat the adverse event, the outcome, whether the event was an SAE, whether it led to withdrawal and whether it is a TEAE. Listings will be sorted by subject identification number, onset date, SOC, and PT. If the onset date is completely missing, then these events will be presented first. If the onset date is missing a month or a day, then these events will be presented before any complete dates.

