A decision to discontinue or temporarily interrupt the study drug for a subject will be considered based on following criteria:

- If ALT/AST baseline measurements (BLM) are <2 x ULN, discontinue if ALT or AST increases to >5 x BLM;
- If ALT/AST BLM \geq 2 x ULN but <5 x ULN, discontinue if ALT or AST increases to 3 x BLM;
- If ALT/AST BLM \geq 5 x ULN, discontinue if ALT or AST increases to >2 x BLM AND the increase is accompanied by a concomitant increase in TBL to >2 x BLM OR the International Normalized Ratio (INR) concomitantly increases by >0.2;
- Any subjects with signs and symptoms of fatigue, nausea, vomiting, right upper quadrant pain or tenderness, fever, and/or rash, accompanied by a >5% increase in eosinophils;
- Subjects who miss more than 2 consecutive QD doses of study drug. Subjects may be replaced unless a stopping rule precludes replacement.

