7.7.3. Pharmacokinetic Criteria for Dose Adjustment

Dose adjustment is not available for subjects in Cohort A receiving 75 mg of CV431 QD. If a patient demonstrates adverse events that trigger the need for stopping, that patient will be stopped and an additional patient will be started on the same dose unless the study data indicates a problem with the dose level as recommended by the DSMB. Subjects in Cohort C, receiving 225 mg of CRV431 QD, experiencing a drug exposure related Grade 3,4 or 5 CTCAE can have a dosage reduction to 150 mg of CRV431 once daily.

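### The SAP tabulates adverse events leading to study withdrawal but not those leading to dose reduction, interruption or stopping of study drug, so where protocol 7.7.3 is applied the withdrawal rate is not comparable between Cohorts A and C

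*Combined protocol and SAP*

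**What the plan says.** **What is summarized.** SAP 7.2.5 plans an overall TEAE table and tables by SOC and PT. They include "the number and percentage of subjects experiencing a TEAE by SOC, PT and the highest severity", "the number and percentage of subjects experiencing a TEAE by SOC, PT and the strongest relationship to study medication", treatment-emergent SAEs, and "the number and percentage of subjects experiencing a TEAE leading to study withdrawal by SOC and PT". Appendix B lists the same set. Study withdrawal is the only treatment consequence tabulated.

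**What is listed.** The AE listing in SAP 7.2.5 has enumerated fields. They cover severity, relationship, any therapy given for the event and the outcome, and they end with "whether the event was an SAE, whether it led to withdrawal and whether it is a TEAE". Action taken with study drug is not among them.

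**What is collected.** Under protocol 11.4 the investigator reports, among other items, "severity, causality, action taken, serious outcome (if applicable), and whether or not it caused the subject to discontinue the study". Action taken and study discontinuation are thus separate items.

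**What can happen to a subject's treatment.**
- Protocol 7.7.1, with no limit by cohort: "A decision to discontinue or temporarily interrupt the study drug for a subject will be considered based on following criteria".
- Protocol 7.7.3 for 75 mg: "Dose adjustment is not available for subjects in Cohort A receiving 75 mg".
- Protocol 7.7.3 for 225 mg: a Cohort C subject with an exposure-related event of Grade 3, 4 or 5 "can have a dosage reduction to 150 mg of CRV431 once daily". No corresponding step is written for either placebo cohort.
- Protocol 8.3.1 makes leaving the study mandatory after a drug-related Grade 3 AE, or a Grade 4 AE of any cause, and makes no exception for Cohort C.

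**The concern.** Tolerability against placebo is part of the first primary objective, and the synopsis names Cohort A versus Cohort C as a comparison for drug effect and dose response. A reader who wants to know how often an adverse event limited treatment will turn to the withdrawal rows, because the SAP offers no others.

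Under protocol 7.7.3 those rows follow different rules at the two doses. A 75 mg subject with a treatment-limiting event has no reduction available. A 225 mg subject with the same event may be reduced and stay in the study, and so never enters the withdrawal count. Any resulting distortion lowers the apparent rate at the higher dose, which is the wrong direction for a trial meant to inform Phase 2B planning.

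The rows also miss interruptions, in every cohort. They count leaving the study, so a subject who stops drug because of an event but remains for follow-up is not clearly captured either.

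**Working it through.** The plan states no figure on this point, and its sample size rests on no statistical calculation, so there is nothing to reproduce. The check is a comparison of sections followed by a short illustration.

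**1. Which treatment changes reach an AE table?**

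| Change caused by an AE | Open to | In an AE summary? | In the AE listing? |
|---|---|---|---|
| Study withdrawal | all cohorts | yes | yes, as a flag |
| Study-drug discontinuation, subject still followed | all cohorts | no | no |
| Temporary interruption (7.7.1) | all cohorts | no | no |
| Dose reduction (7.7.3) | Cohort C only | no | no |

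**2. How far can the withdrawal row drift?** Inputs: 12 subjects planned in each of Cohorts A and C (protocol 7.2). Two quantities are assumed: p, the true proportion with a treatment-limiting AE, taken as equal in both cohorts; and f, the share of Cohort C cases reduced instead of withdrawn.

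- Expected withdrawals in A: 12p.
- Expected withdrawals in C: 12p(1 − f).

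| p | Cohort A | C, f = 0 | C, f = 0.5 | C, f = 1 |
|---|---|---|---|---|
| 0.10 | 1.2 | 1.2 | 0.6 | 0 |
| 0.20 | 2.4 | 2.4 | 1.2 | 0 |
| 0.30 | 3.6 | 3.6 | 1.8 | 0 |

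The chance of at least one withdrawal is 1 − (1 − q)^12, with q = p in A and q = p(1 − f) in C. At p = 0.20 this is 1 − 0.8^12 = 0.931 in A. In C it is 0.931 for f = 0, 1 − 0.9^12 = 0.718 for f = 0.5, and 0 for f = 1.

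**3. Does a combined count repair it?** If withdrawal, reduction and interruption are counted together, each cohort expects 12p (1.2, 2.4 or 3.6) whatever f is.

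**4. What do the other outputs recover?** The severity and relationship tables count an event regardless of the action taken, so a Grade 3 or higher event in a reduced Cohort C subject is still there, at 12p in both cohorts. Exposure (SAP 7.1) shows the reduction itself. Full dosing at 225 mg is 28 × 3 = 84 capsules; a subject reduced to two capsules from Day 15 takes 14 × 3 + 14 × 2 = 70. Neither output says which event caused the change.

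**5. Which protocol rule sets f?** If 7.7.3 is followed, f can lie anywhere from 0 to 1. If 8.3.1 is followed, f = 0 for drug-related Grade 3 and all Grade 4 events, and the A versus C asymmetry largely disappears. Both sections are current text, so the documents do not settle f.

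**The case against.** A reader might infer that the SAP counts an intolerable event only when the subject withdraws, so that the same toxicity is seen at 75 mg and vanishes at 225 mg. The documents do not support that. Reduction is offered only for exposure-related events of Grade 3 or above, and such events enter the severity, relationship and SOC/PT tables and the listing of all AEs. The reduced capsule count is in the exposure data.

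It is also tempting to quote 3 of 12 (25%) in Cohort A against 0 of 12 in Cohort C as the size of the bias. That is the f = 1 extreme at p = 0.25, and f = 0 gives no bias. It also ignores replacement: three withdrawn subjects who are replaced give 3/15 = 20% of the Safety Set, before counting any event in a replacement. Three subjects with the same Grade 3 event attributed to drug would stop the study for review under protocol 7.7.2.1, so such a cluster would not pass unnoticed.

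Further points count against a strong reading. Protocol 8.3.1, if it governs, removes most of the asymmetry. Interruption is open to every cohort, so missing it creates no built-in bias between A and C. The safety analysis is descriptive, and the SAP does not designate withdrawal as its tolerability measure.

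All of this stands and limits the point. Three things remain. The contradiction between 7.7.3 and 8.3.1 leaves f uncontrolled. Severity does not replace treatment consequence: a Grade 3 count cannot show which events changed dosing, and one interruption trigger in 7.7.1 (symptoms such as fatigue, nausea or rash with an eosinophil rise) carries no grade threshold. And action taken is collected, yet no output is planned for it.

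**Conclusion.** The point holds as a reporting gap with a conditional bias. The SAP has no summary of TEAEs leading to dose reduction, interruption or study-drug discontinuation, and its AE listing leaves out action taken. That is certain from the text; the AE section of the SAP is not redacted.

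Where 7.7.3 is applied, the withdrawal rate understates treatment-limiting toxicity in Cohort C relative to Cohort A, by 12pf expected subjects out of 12. At an assumed p = 0.20 that is 0, 1.2 or 2.4 subjects for f = 0, 0.5 or 1. This rests on equal true rates, cohorts of 12 without replacement, and values of p and f that the documents do not give. The events themselves remain visible. The loss is the link from event to dose change, and a treatment-limiting rate that means the same thing in each cohort.

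The importance is moderate. No test depends on it, but it bears on a primary objective and a named dose comparison, and it is cheap to correct.

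**What to change.** **SAP 7.2.5 and Appendix B.** Add one table, by cohort, giving counts and percentages of subjects whose TEAE led to (a) study-drug discontinuation, (b) interruption, (c) dose reduction, and (d) any of these. Show row (d) next to the withdrawal row for the Cohort A versus C and active versus placebo tolerability comparisons. Add action taken with study drug to the AE listing.

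**Cost.** One table and one listing column. Protocol 11.4 already collects action taken for each AE. The CRF is not among the documents, so the sponsor should confirm that its categories separate interruption, reduction and discontinuation.

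**Protocol, separately.** Sections 7.7.3 and 8.3.1 contradict each other on what follows a high-grade drug-related event in Cohort C, and the sponsor must reconcile them. Which rule governs is the sponsor's decision. The reconciliation should also state how any remaining change in capsule number affects the subject blind. Under protocol 7.3.3 that is the trial's only blind, and 7.7.3 as written provides a change in capsule number only for subjects on active drug.
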